7.7 Therapist Training and Ongoing Consultation

Existing therapists and clinical supervisors from across the four participating pediatric health networks will be trained by the study team to deliver CBT for youth anxiety. Consistent with best practices for promoting quality implementation of evidence-based treatment,¹⁰⁷⁻¹¹⁰ a

multi-component strategy is to be used that involves training workshops for therapists and supervisors, followed by asynchronous online resources and ongoing small group consultation of therapists and supervisors. The same therapists are to participate in care across both treatment comparators.

7.7.1 Training workshop. Prior to treating patients on the Kids FACE FEARS trial, therapists and supervisors will participate in one full-day (8 hour) training or two half-day (4-hour) trainings. These trainings will be led by members of the Training, Fidelity and Sustainability Core (e.g., [name], [name], [name], [name], [name], and [name], LICSW). Those attending these trainings should be natural providers and supervisors in the pediatric health settings participating in the trial (i.e., clinical staff not employed by the research trial and not working in anxiety specialty settings). Trainings can be provided in-person or on Zoom. All clinicians and supervisors will be provided with a full set of Cool Kids treatment workbooks prior to the start of the training. Trainings will incorporate didactic components and active teaching approaches (e.g., live role-plays, demonstrations of core skills, small break-out groups, interactive video presentations, opportunities for therapists to actively practice using specific CBT skills to treat child anxiety).

Trainings are to start with an introduction to the trial, followed by: (a) overviews of the core principles of CBT for youth anxiety, (b) detailed, step-by-step instructions in how to deliver the core skills in the Cool Kids and Chilled therapy protocols (e.g., psychoeducation, cognitive restructuring, exposure, and parenting anxious behaviors), and (c) additional coping skills such as problem solving, social skills building, and progressive muscle relaxation. Therapists and supervisors are taught about the adaptive and unhelpful aspects of anxiety, factors that maintain youth anxiety, and evidence-based strategies for offsetting these factors. Trainings will also emphasize the importance of caregiver involvement in treatment (as appropriate, and when feasible), between-session practice, and treatment fidelity within flexibility.^{69,111} Moreover, therapists and supervisors will be provided guidance on addressing common treatment barriers, such as lack of between-session practice or poor treatment attendance, and how to problem-solve and support families through various challenges that can emerge during treatment.

These trainings will also include a demonstration of the guided online programs (including illustrative video clips and how to log in and access the online materials) and will incorporate direct instruction on how to conduct check-in calls for the guided online treatment condition. Therapists and supervisors will be provided with a check-in call conversation guidelines/scripts to follow (see description of Comparator 2, above), and will be taught how to navigate common questions.

After each training, therapists and supervisors will complete post-training knowledge quizzes. Any therapist who scores <80% on the post-training knowledge quiz will receive individualized follow-up training and support, and will then be retested with an alternate form of the knowledge quiz, and will be required to meet the 80% training criterion prior to treating patients in the study.

7.7.2 Asynchronous online resources. After each training, therapists and supervisors will be provided resources to support their delivery of the treatment comparators, including session outlines, training recordings and booster supports as needed. In response to requests from therapists and supervisors, a website with helpful resources has been developed to further support therapists as they implement treatment. This website includes treatment demonstration videos, treatment module summaries, and therapist training slides. A guided refresher course was created and is included on the website that includes audio and video training demonstration videos and interactive training activities.

7.7.3 Consultation and support. Providers (therapists and supervisors) at the study performance sites will participate in regularly held group consultation videoconferencing calls led by experts in the treatment of pediatric anxiety. These consultation calls will be held in addition to any routine supervision that may be naturally afforded to providers in their local hospital or clinical network.

All participants who attend a training workshop will be assigned to a recurring consultation call group. Therapist consultation calls will be held biweekly (i.e., twice monthly). These calls are designed to support therapists on the project, to prevent therapist drift, and to afford education and scaffolding to providers. Approximately 4-6 therapists are to be assigned to each call group. The remote format enables consultation call groups to contain a mix of therapists from across study sites and regions. Calls will each be one hour, and will be used to clarify and role-play therapy skills, to answer any questions about the two treatment formats, and to support therapists as they implement the treatments. Site supervisors will also participate in a separate, once-monthly supervisor group consultation call, also led by an expert in pediatric anxiety treatment.

Each consultation call will be structured to formally review a specific rotating skill or topic, including: psychoeducation, fear hierarchies and exposures, cognitive strategies, cultural considerations, parenting factors, check-in calls, homework compliance, general coping skills, treatment flexibility, COVID-related anxiety, school anxiety, developmental considerations, and technology-related issues. Each call will also include a “Therapist Spotlight,” in which a rotating therapist will have an opportunity to receive more individualized attention and in-depth consultation about one of their patients. These Therapist Spotlights give call leaders the opportunity to clarify and correct any potential

problems with treatment delivery, and to provide individualized follow-up training and support to therapists as needed. Therapist spotlights also provide opportunities for therapists to provide peer input to one another and to learn from one another's experience and perspectives.

7.8 Safety, Reaction Management, and Clinical Deterioration

All study participants will be working with trained therapists who can assist participants if they were to become upset. If a participant becomes upset during the process of being interviewed and/or while completing assessment measures with an RA (Research Assistant), the RA will ask if the participant/ family would like to check-in with their doctor or one of the clinicians with behavioral health training at the site. Participants will also be provided with the phone numbers of their site research staff who they can contact if they become upset while completing the assessments online. The research staff will connect them with an available clinician in these situations. The study facility will be appropriate to children, as these facilities will be pediatric healthcare sites. We will make sure that all psycho-educational materials, treatment plans are written in a straightforward manner, at the appropriate literacy level. We will use translators/language line as needed to further ensure guardians fully understand study procedures and communicate concerns about their child's care.

As all site staff and the investigators are mandated reporters, families will be informed that any disclosure of abuse, risk to a child or elder will need to be reported to the appropriate state protection agency. Endorsement of suicidality, risk to self or others will require emergency evaluation for safety and disposition by the clinical staff and RAs will have a contact at each site for reporting such disclosures and to activate the clinical protocol for these types of events. RAs will also contact the study PIs and report the event to the lead site and for inclusion in reports to the DSMB.

7.8.1 Safety policy

The study intervention does not pose an additional risk to pregnant women and so pregnant women (guardians or youth participants) can be enrolled in the study.

Therapist concern for patient mental health severity and/or safety:

If the child's therapist has concerns over the safety of the child or their current severity of illness, the therapist will report their concerns to the site clinical supervisor and a decision regarding the needed level of care (e.g., inpatient, acute care) will be made based on a

Study: Kids FACE FEARS

clinical determination. The team will then report this to the study PIs to discuss if the child should be removed from the study.

Research assistant concern for patient mental health severity and/or safety:

If the PROMIS Short Form for Anxiety shows an increase of 5 points on the T-score metric at an assessment point (or the equivalent of 0.5 standard deviation which is a clinically meaningful difference) (Norman, Sloan, & Wyrwich, 2003), the local RA will notify the participant's therapist. Their therapist will discuss with the clinical supervisor and site PI if the participant should be removed from the study and referred to a different model of care or level of treatment.

If the DASS-21 completed by guardians shows severe or extremely severe in any dimension of the assessment (depression, anxiety, stress) or if the guardian marks a score of 2 or 3 on item 21 ("I feel that life is meaningless") at an assessment point, the RA will notify the family's therapist (Lovibond & Lovibond, 1995). Their therapist will discuss the appropriate course of action with the site supervisor for clinical determination to ensure the safety and well-being of the child and guardian. The clinical team will again discuss with the PI if family should be removed from the study.

Examples of situations where family/ child may need to be removed from the study include: emergence of a psychotic disorder, need for prolonged residential placement, youth detention, suicidal behavior, parental/ guardian psychiatric hospitalization. Clinical decision making will be the first principle for addressing family treatment needs for any worsening mental health severity, safety and functioning.

REDCap will automatically send an email to the local RA at each site whenever a score is flagged on either measures.

Telehealth and Zoom Videoconferencing

In order to protect patients during pandemics, such as COVID-19, patients and participants will have to option to complete study visits via Zoom Video Communications software. This will be provided as an option for study visits/ procedures including consent procedures, PARS baseline assessments, and technical orientation. Zoom Video Communications is a remote conferencing services company that provides remote conferencing services, that combines video conferencing, screen sharing services, online meetings, chat, and mobile collaboration, with both audio and video communication options. Participants can use zoom via their phone, computer, or tablet/Ipad. Study visits will not be recorded.

If the participant's preference is for videoconference, the RA will send the participant a link to a Zoom meeting, along with a link to the Zoom Privacy Policy. The RA will also send instructions on how to use Zoom, including guidance on best practices for sharing as little personal information with Zoom as possible. These best practices will be: (1) suggesting that the participant only enter their first name instead of their full name, and (2) if they don't want to give their email, that they should feel free to use [contact]<mailto:[contact]> as their email address. The link to join the Zoom meeting will only be accessible by the RA conducting the visit and the patient or participant. The RA will complete the video conference in a private room, and the meeting will not be recorded. If a participant is not comfortable with using the Zoom software, they will always have the option to call-in to the meeting via phone, or meet in-person.

7.8.2 Removal of Participants. All instances of study dropout will be documented using a Premature Termination form on REDCap including the reason for dropout, who decided that the participant would drop out (i.e., parent or guardian, therapist, study staff, adolescent patient), and whether the dropout resulted from burden of intervention, study assessment, or both. Withdrawn participants will be encouraged to continue to participate in study assessments throughout the 1-year follow-up period in order to optimize the intention-to-treat assessment design. Participants may withdraw voluntarily at any time for any reason.

There are two types of participant withdrawal: "treatment withdrawal" and "study withdrawal."

1. **Treatment withdrawal** is when a participant drops out of treatment (either because they are no longer interested or because a clinician or study investigator feels that treatment is no longer appropriate), but still provides the research team with posttreatment data by completing assessments at post treatment and Week 52.
2. **Study withdrawal** is when a participant (or a provider on behalf of the participant) explicitly communicates that they are no longer interested in being a part of the study at all – including future assessments and compensation. Cases of "treatment withdrawal" are not automatically considered to be "study withdrawal" unless the participant specifically states that they never want to be contacted again by the study, or if a clinician or study investigator deems that any future contact would be inappropriate.

Participants may be removed if:

- If the participant's provider or therapists feels the study is negatively impacting the participant's health or wellbeing resulting in increasing severity of illness that is clinical assessed as such by the therapist/ provider team. Such cases will be

assessed clinically, and an appropriate treatment plan will be determined and then discussed with the PI for determination of whether patient should be removed from study.

- If there is an increase in the participant's anxiety levels based on the PROMIS Pediatric Short Form for Anxiety and or other worsening of mental health status that leads to change in the treatment plan/ level of care determination by clinical team.
- If the participant becomes suicidal and presents with clinically determined safety risk to self or others.

If staff or therapists participating in the study leave the participating clinical site, they will be asked to complete 1 follow up assessment before leaving. Once they leave employment at the site, they will be removed from the study.

7.8.3 Data Safety Monitoring Plan. The study PIs, [name] and [name], will be responsible for monitoring the study and will do so in the following way:

- (1) They will continuously assess protection of data and participant confidentiality. If any breach in the protection of participant data is identified or breach of confidentiality, it will be reported as an adverse event to the lead site and be assessed to determine if the event relates to the study and requires any protocol changes or study-wide action to ensure the protection of patient data.
- (2) They will meet with site PIs on a monthly basis to review study progress and elicit any concerns. They will be charged with minimizing any risk involved with participation, monitoring the risks and benefits during implementation of the project on a timely basis, and ensuring that the research is conducted according to high scientific and ethical standards.

The principal investigators will also report the findings to the PCORI program staff. PCORI will be informed of any actions taken by the IRB as a result of their continuing review.

In addition, a **Data Safety and Monitoring Board (DSMB)** will meet twice annually to provide independent oversight of data management and integrity, and participant safety.

Data Safety and Monitoring Board Co-Chairs: [name] is Associate Professor of Psychology at Boston University and Director of the Family Development and Treatment Program; she is a renowned expert in the family-based treatment of pediatric mood and anxiety problems, and has extensive experience leading randomized clinical trials. [name] is Professor of Psychology at Florida International University and a leading expert on child development and individual differences. The Co-Chairs will

meet twice annually to independently review and evaluate study data for participant safety, study conduct, progress, and efficacy, and make recommendations for modifications if needed.

7.8.4 Adverse Events Definition and Reporting. Potential Adverse events are defined as potential physical, emotional, legal or financial risk. We do not foresee any physical, legal, or financial risk for any of the study participants.

The following definitions will be used in the assessment of safety:

Adverse Event (AE) is any abnormal or harmful behaviors, increasing severity of symptoms that are identified by the therapist, suicidal behaviors or attempts, breach in the protection of participant data or breach of confidentiality whether or not considered related to the participants' participation in the research.

Serious Adverse Event (SAE) is any adverse event that

- (1) results in death;
- (2) is life-threatening;
- (3) results in inpatient hospitalization or prolongation of existing hospitalization;
- (4) results in a persistent or significant disability/incapacity;
- (5) based upon appropriate medical judgment, may jeopardize the participant's health and well-being and requires hospitalization, other mental health or medical stabilization, child protection services or other higher level of care.

Life-threatening means that the event places the participant at immediate risk of death from the event as it occurred.

Unanticipated Problem is defined as an event, experience or outcome that meets **all three** of the following criteria:

- is unexpected; AND
- is related or possibly related to participation in the research; AND
- suggests that the research places participants or others at a greater risk of harm (including physical, psychological, economic, or social harm) than was previously known or recognized.

Possibly related means there is a reasonable possibility that the incident, experience, or outcome may have been caused by the procedures involved in the research.

Unexpected means the nature, severity, or frequency of the event is not consistent with either:

- the known or foreseeable risk of adverse events associated with the procedures involved in the research that are described in (a) the protocol-related documents, such as the IRB-approved research protocol, any applicable investigator brochure, and the current IRB-approved informed consent document, and (b) other relevant sources of information, such as product labeling and package inserts; or
- the expected natural progression of any underlying disease, disorder, or condition of the participant(s) experiencing the adverse event and the participant's predisposing risk factor profile for the adverse event.

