Although a number of established and highly overlapping Therapist-Led CBTs for youth anxiety exist, the well-supported *Cool Kids* CBT suite for youth anxiety^{99,100} was selected for several important reasons. First, *Cool Kids* includes all the “gold standard” CBT components for treating youth anxiety and has an extensive research base.^{101–103} Second, *Cool Kids* is a time-limited and relatively brief suite of treatment programs delivered across roughly 3 months, which accommodated the PFAC and stakeholder advisor suggestion for relatively short-term treatment. Third, the *Cool Kids* suite of treatment programs comprehensively includes developmentally tailored versions for the full age range of youth included in the study (7–18 years). Fourth, the *Cool Kids* treatment suite has a documented history of successful implementation when rolled out on large-scale levels.^{103,104} Fifth, a parallel self-administered online version of *Cool Kids* teaches youth the same anxiety management skills as the therapist-led version, and in a roughly comparable number of sessions/modules, thus allowing for well-matched and time-equitable comparisons. And finally, the *Cool Kids* therapist-led and online treatment programs are all available in English and in Spanish.

The standard *Therapist-Led Cool Kids Therapy for Anxiety (ages 7-12)*⁹⁹ is a structured, evidence-based, 10-session program for treating youth anxiety in middle childhood and entails ten 50-minute weekly sessions with children and families. Therapists teach youth and caregivers core CBT components including anxiety psychoeducation, cognitive/coping skills for thinking more realistically and adaptively, problem-solving skills, and graded exposures to anxiety provoking situations. Caregivers and youth are taught skills for managing anxiety and for reducing avoidant behaviors. Caregivers are included in all sessions (adjusted developmentally) and are taught parenting skills plus personal anxiety management. The program is supported by

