To foster supportive accountability and engagement,^{67,68} families in this condition receive brief phone check-in calls (i.e., < 15 minutes) from a therapist every other week. To ensure these brief calls do not drift into treatment sessions, therapists work from a conversation guideline to standardize calls (with space for flexibility as appropriate). Therapists should begin each check-in call with an explanation of the purpose of the call—i.e., to see how their use of the online modules is going, to find out whether the child/teen/caregiver has any questions, to support the family with the program, and to make a plan for continued practice. Therapists then check in briefly about each of the following components: (a) engagement with online program and activity completion (“Were you able to log into the online program? If not, what got in the way?”); (b)

identification of current difficulties/barriers, including technical or motivational challenges (“Did anything get in the way of completing activities or practice? Did you experience any difficulties as a parent with respect to your child/teen’s anxiety management?”); (c) brainstorming possible solutions to identified barriers (“Let’s see if we can problem-solve together and come up with some solutions to help you complete materials this week”); (d) review of anxiety and caregiver progress (“Has your/your child’s level of anxiety changed since beginning the program?); (e) technical questions about content (“Do you have any specific questions about the material that you learned in the modules you completed?”); (f) assignment/plan for next two weeks, providing encouragement and praise for even small successes; and (g) confirmation of the next call.

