Treatment fit and flexibility. As part of the *Session Summary Form* completed by the therapist after each treatment session (for Therapist-Led CBT cases) or check-in call session (for Guided Online CBT cases), therapists will indicate their level of agreement with the following statement on a scale from 0 (*not at all*) to 6 (*extensively*): "To what extent was the content covered this [session/check-in call] a fit to this child's clinical presentation and individual needs?" To assess needs for treatment flexibility, therapists will also indicate after each session their level of agreement with the following statement on a scale from 0 (*not at all*) to 6 (*extensively*): "How much did you need to tailor or adapt the content or structure of this session because of the child's clinical presentation and individual needs?" Moreover, as part of the *Session Summary Form*, therapists will select the reason(s) they may have covered content outside of the treatment protocol in the session they just held from a list of options (if relevant): (a) had to address a clinical emergency that made them concerned about immediate safety, (b) needed to

address a topic of the week that did not directly relate to the focus of the treatment protocol (e.g., family conflict, school trouble), (c) had to address a co-occurring/co-presenting issue other than child anxiety (e.g., ADHD, medical problem), (d) needed to engage in an alliance-building activity, (e) needed to address treatment resistance, (f) other (describe).

Treatment engagement and barriers. Therapists will complete weekly logs reporting whether study families on their caseloads attended their scheduled sessions or support calls and whether they completed the homework assigned in their previous session or support call. These data will be used to characterize *Treatment Attendance* and *Homework Engagement*. *Treatment Completion* is defined for Therapist-Led CBT as attending 10 treatment sessions, and for Guided Online CBT Care as attending 4 support calls. For Guided Online CBT families, administrative backend data will also be collected from the central server to further assess user/usage analytics.

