7.15.1.1 Therapist Contacts During the Treatment Phase for Guided Online CBT

Participants. Before the beginning of treatment in the guided online CBT arm, the following points of engagement must occur:

1. The therapist providing supportive accountability for the case must reach out to the patient over the phone or online to introduce themselves to boost patient engagement.
2. A technical orientation on the self-paced online program must take place with the participant. The technical orientation will be conducted using tools provided by the lead site. This orientation will go over how to navigate the program and who to contact with technical issues. This orientation can be conducted in-person, over the phone or via videoconference using Zoom software. The participant will always be

given the option to either attend the orientation in-person, on the phone, or via videoconferencing.

3. Participating families in this condition are given up to 20 weeks (i.e., the treatment phase) to complete their treatment program.
4. The therapist will work with the participant (and/or their family) to schedule check-in calls every 2 weeks. Throughout the duration of the program, these check-in calls will be held with the family or caregiver for children ages 7-12, and will be held with the child for children ages 13-18.
5. The participating family is guided to complete one self-administered module of the program each week. Families are encouraged to revisit and review completed modules as frequently as they wish.
6. The therapist will call the guardian and/or child every 2 weeks to check-in and provide supportive accountability. For each scheduled check-in/supportive accountability call, therapists should make at least 3 attempts to contact the family.
7. Therapists are to complete will complete a brief session log on REDCap after every check-in/supportive accountability call.

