7.15.1.2 Therapist Contacts During the Treatment Phase for Therapist-led CBT Participants

1. Participating families in this condition are given up to 20 weeks (i.e., the treatment phase) to complete their treatment program.
2. Each therapy session should be scheduled for 50-60 minutes. Therapists are advised to schedule families for roughly one therapy session per week.
3. Therapists can schedule multiple sessions a given week to help “catch up” if cancellations, missed appointments, holidays, or schedule breaks places them behind schedule.
4. Therapists are to complete will complete a brief session log on REDCap after after every treatment session.

*All clinics will work with their team to establish a workflow that is conducive to the procedures established above. This workflow will be shared with the lead site and any changes will be reported within a week of implementing the updated workflow.

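### Adverse-event recording of symptom worsening rests on therapist identification, which is unequal by arm; a by-arm PROMIS deterioration table should sit beside it

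*Combined protocol and SAP*

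**What the plan says.** Section 7.8.4 defines an AE through a short list: abnormal or harmful behavior, "increasing severity of symptoms that are identified by the therapist", suicidal behavior or attempts, and data or confidentiality breaches. Only the symptom-worsening item names an observer.

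Contact with that observer is set by arm:

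- **Therapist-Led CBT.** Section 7.2 describes a program that "entails ten 50-minute weekly sessions with children and families" for ages 7-12, and ten sessions for adolescents as well. Section 7.15.1.2 adds: "Each therapy session should be scheduled for 50-60 minutes".
- **Guided Online CBT.** Section 7.2 provides "brief phone check-in calls (i.e., < 15 minutes) from a therapist every other week". Section 7.6.3 defines completion "for Guided Online CBT Care as attending 4 support calls". Section 7.15.1.1 says "Participating families in this condition are given up to 20 weeks" to finish. It also places the calls with the family or caregiver for ages 7-12, and with the young person from age 13.

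Section 7.8.1 has a second route that does not depend on arm. "If the PROMIS Short Form for Anxiety shows an increase of 5 points on the T-score metric at an assessment point", REDCap alerts the local research assistant, who tells the therapist; removal or referral is then discussed. Neither section 7.8.1 nor the reporting plan in 7.8.5 says that such a flag is recorded as an AE. Section 7.16 contains no analysis of AEs or of deterioration by arm.

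**The concern.** In a trial of anxiety treatment, symptom worsening is the harm most directly tied to the treatment being compared. If its recording depends on an observer who meets one arm for hours and the other for short calls, equal true worsening can give unequal AE counts. Section 7.7 has the same therapists work in both arms, so the imbalance comes from contact and not from personnel.

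Two uses of the data are exposed. The DSMB reviews participant safety twice a year (sections 5 and 7.8.3), and results are to be reported under CONSORT (section 7.16). A by-arm AE table in either place would carry the imbalance, and the plan sets no measure of worsening beside it that is collected in the same way in both arms.

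**Working it through.** The documents give no total contact time, expected AE rate or AE comparison, so there is no stated figure to reproduce.

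**Step 1. Planned contact (contacts × minutes per contact).**

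| | Contacts | Minutes each | Total |
|---|---|---|---|
| Therapist-Led | 10 | 50-60 | 10 × 50 = 500 to 10 × 60 = 600 |
| Guided Online, on pace | 4 (8 weekly modules, one call per 2 weeks) | under 15 | 4 × 15 = 60, so under 60 |
| Guided Online, full window | 20 / 2 = 10 | under 15 | 10 × 15 = 150, so under 150 |

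The online totals leave out one introductory contact of unstated length (section 7.15.1.1), which does not change the contrast. At ten calls the number of contacts is equal and only their length differs.

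**Step 2. What this could do to recorded counts.** This is an illustration on assumptions. Let each contact detect existing worsening with probability p, so that detection over k contacts is 1 − (1 − p)^k. Assume equal true worsening in both arms, and p = 0.1 or 0.2.

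- p = 0.1: 10 sessions 1 − 0.9^10 = 0.651; 4 calls 1 − 0.9^4 = 0.344; ratio 0.53.
- p = 0.2: 10 sessions 1 − 0.8^10 = 0.893; 4 calls 1 − 0.8^4 = 0.590; ratio 0.66.
- 10 calls, same p: ratio 1.

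With true worsening of 20% in 150 per arm (30 children) and p = 0.2, recorded events would be 30 × 0.893 = 26.8 against 30 × 0.590 = 17.7. The model treats a call of under 15 minutes as equal to a full session. If a call detects less, the ratio is lower.

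**Step 3. Effect of the PROMIS flag, if flags became AE records.** Let flags capture a share q of worsening independently, so that recording is 1 − (1 − detection)(1 − q).

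- q = 0.5: ratios 0.81 (p = 0.1) and 0.84 (p = 0.2).
- q = 0.8: ratios 0.93 and 0.94.

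Whether flags are recorded therefore matters more than the choice of p.

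**Step 4. Would a PROMIS-based measure have usable counts?** Section 7.8.1 equates 5 T-points with half a standard deviation, so SD = 10. The SD of change is 10 × √(2(1 − r)). Assume a mean improvement of 5 points; a rise of 5 or more then lies 10 points above the mean change.

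- r = 0.5 (the correlation in section 7.16.1): SD 10.0, proportion 0.159.
- r = 0.6 (assumed): SD 8.9, proportion 0.132.
- r = 0.7 (assumed): SD 7.7, proportion 0.098.

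About 10-16% per visit would meet the criterion. Taking 13.2% in both arms, the 95% half-width for the difference is 1.96 × √(2 × 0.132 × 0.868 / n). That gives ±7.7 percentage points at n = 150 per arm, ±9.2 at 105 (30% attrition) and ±10.8 at 75 (50% attrition). The table is descriptive with an interval, not a powered safety test.

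**The case against.** The strongest reply is that detection does not depend on minutes alone. Section 7.6.2 has therapists rate global improvement against baseline after every session and every call. The call guide in section 7.2 asks whether anxiety has changed since the program began. PROMIS flags reach the therapist in both arms and can prompt identification. All of this stands, and it is why no size can be given.

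Four stronger readings are tempting, and the documents do not support them.

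- **That counts will differ 3- to 10-fold.** The contact minutes do (500/150 = 3.3; 600/60 = 10), but nothing says detection is proportional to minutes. A rate per contact hour would build in the same assumption.
- **That worsening can surface only through therapist contact.** Risk disclosures to research assistants go to the PIs, the lead site and the DSMB reports (section 7.8). Suicidal and harmful behavior carry no therapist condition, and serious events turn on consequences such as hospitalization.
- **That the PROMIS flag is only a notice.** It starts a discussion of removal or referral, and a PROMIS increase that leads to a changed treatment plan is a listed removal reason (section 7.8.2). What is missing is a statement that it is recorded as an AE, and a tabulation by arm.
- **That Guided Online is certain to look safer.** The direction is likely, not established. No between-arm AE test is planned, so no specified inference is biased.

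It can also be said that PROMIS is already compared between arms as a primary outcome, with family improvement ratings and masked PARS beside it. That is true, but the planned models compare average trajectories and response. None reports the share of children who got worse. The caregiver-held calls for ages 7-12 add little to the concern, since caregiver report is the one required to randomize that age group (section 7.6).

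**Conclusion.** The point holds in a limited form. As written, the symptom-worsening component of the AE definition depends on an observer whose planned contact is 500-600 minutes in one arm and under 60-150 minutes in the other. Ascertainment is therefore unequal and probably favors Guided Online.

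The size is unknown. The ratios of 0.53-0.66 rest on four calls, equal true worsening, equal detection per contact and no recording of flags. They move to 0.81-0.94 if flags are recorded and capture 50-80% of worsening, and to 1 with ten calls and equal detection per contact. None of these inputs is in the documents. The other AE components are not affected in this way. This is an inexpensive improvement to harm reporting, not a flaw in the efficacy comparison.

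**What to change.** Pre-specify one table for the DSMB and the final report: the proportion of children in each arm whose PROMIS T-score is 5 or more points above baseline at midtreatment, posttreatment and Week 52, separately for caregiver and youth report, with the between-arm difference and its confidence interval.

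- Compute it from the scores and not from the REDCap flags, because section 7.8.1 does not say whether the rise is measured from baseline or from the preceding assessment, or which informant counts.
- Give the number assessed per arm, informant and visit. Baseline reports from both informants are not required for randomization, and 7-year-olds give no self-report. Handle missing scores with the planned multiple imputation.
- Show the table beside therapist-identified AEs, with a note on the unequal planned contact.
- State in section 7.8.4 or 7.8.5 whether a PROMIS flag is recorded as an AE, with the same rule in both arms.

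The cost is one table from data already collected. Some counted rises will be measurement error, in both arms. The measure also depends on completed assessments, and section 7.15.4 expects 30-50% attrition by final follow-up, so the Week 52 row will be the weakest. Clinical handling of a flag does not change.
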